## 1.0 Background & Rationale

Motor learning is defined as the process that occurs in the brain aimed at developing new movements with practice until they can be performed automatically (Schimdt & Wrisberg 2008). Motor skill improvement is best noted by a change in the speed-accuracy function, meaning execution of motor patterns occurring more accurately at different speed ranges (Kantak et al., 2017; Reis et al., 2009). Learning motor skills necessitates the interaction of several high-level cognitive processes with low-level sensorimotor mechanisms (Krakauer & Mazzoni, 2011). A complex neuroanatomical architecture supports the learning and retention of motor skills, which includes increased activation in the frontoparietal cortices like dorsolateral prefrontal cortex (DLPFC), primary motor cortex, and posterior parietal cortex (PPC), and subcortical structures like the cerebellum and basal ganglia, which show increased activation during the later stage of short-term motor learning (Floyer-Lea & Matthews, 2005; Halsband & Lange, 2006).

Motor skill learning involves not only changes in the motor system, but also depends on sensory systems. One of the sensory modalities critically important for motor skill is position sense or proprioception. It is the ability of an individual to integrate sensory inputs from the muscles and joints to determine the positions and movements of body segments in space (Han et al., 2016). The proprioceptive information about the hand's position is taken into consideration by the motor system as feedback which is required for smooth and skilled movement execution (Bossom, 1974; Jeannerod, 1988). Many studies have shown that an enhancement in proprioception results in improvements in motor learning/decline in motor deficits or vice versa, although the neural basis of such interactions is unclear. In addition to acting as an interface between the sensory and motor cortex, posterior parietal cortex (PPC) is thought to play a role in processing higher-level proprioceptive information (Amaral, 2013). Stroke research has revealed the critical involvement of PPC, specifically supramarginal gyrus (SMG) in processing the sense of position (Findlater et al., 2016). A study by Ben-Shabat et al., 2015, found a key role of SMG in proprioception. They suggested that in patients with stroke, decrease in proprioception might be associated with decrease in right SMG function which might be due to SMG's role in motor control and spatial processing (Ben-Shabat et al., 2015). However, it is unclear how SMG modulates proprioceptive functioning to affect motor skill learning.

Research has also found an indirect connection between DLPFC and proprioception. Stagg et al., (2013) applied anodal tDCS over left DLPFC and found an enhanced functional connectivity between sensorimotor cortex and DLPFC. They further suggested that the enhanced activity in the DLPFC might be linked to enhanced proprioception. Beck et al., (2019) also found an increased activity in the sensorimotor cortex possibly through the fronto-striato-thalamic pathways after applying anodal tDCS over DLPFC suggesting that DLPFC might be involved in enhancing proprioception in healthy individuals. They proposed that DLPFC can be used as a potential target in neurorehabilitation in patients with motor deficits (Beck et al., 2019).

The sensorimotor network associated with proprioception and motor skill learning is not fully understood, and the functional role of activity in high-level areas such as DLPFC and SMG is particularly unclear. With greater knowledge of these processes in the healthy brain, it may one day be possible to develop rehabilitation strategies that target a patient's unique mix of sensory and motor deficits.

## 2.0 Objective(s)

The aim of the present study is to test role of activity in SMG and DLPFC in proprioception and motor skill learning. A robust way to identify whether a brain region plays a role in a behavior is to temporarily modulate its excitability in healthy people using non-invasive brain stimulation

(Cohen et al., 1997; Reis et al., 2008). This is commonly done in research with a short sequence of low-intensity transcranial magnetic stimulation (TMS), also known as repetitive TMS (rTMS). A small, temporary reduction in cortical excitability can be achieved through continuous theta burst stimulation (cTBS), a low intensity patterned form of rTMS that is delivered over 40 seconds, with excitability effects lasting up to an hour (Huang et al., 2005). rTMS is used clinically to treat conditions such as depression and is considered very low risk provided the generally accepted screening criteria are met. In the research setting, this technique is widely used not only in healthy adults (as in this study) but also in children and people with concussion, stroke, Parkinson's disease, and more (Rossi et al. 2021).

In separate groups of subjects, we will use a 40-second sequence of rTMS called continuous theta burst stimulation (cTBS) over SMG, DLPFC, or sham (control), before the subject performs tasks known to involve proprioception and either a short or longer sequence of motor skill learning (a maze tracing task). If cTBS over SMG or DLPFC has an impact on task performance for that group (in comparison to the sham, or control group), it suggests activity in that brain region is important for the affected aspect of task performance.

This project has two objectives:

- Objective 1. To explore the role of DLPFC and SMG in proprioception.
- Objective 2. To assess the role of DLPFC and SMG on motor skill learning and proprioceptive changes at two different time scales.

[figure not shown]
Because cTBS is intended to be disruptive, it is possible that the sham group will have the best performance in one or more outcome measures. It is also possible that some aspects of performance will be better in the SMG or DLPFC group due to complexities of the neural networks supporting these behaviors. However, it is not the goal of the study to determine which intervention yields the “best” task performance, it is simply to determine the details of how the DLPFC and SMG groups differ from each other and from the sham group.

### 3.0 Outcome Measures/Endpoints

Outcome measures will be assessed during the main (experimental) session, which takes place on a single day. Proprioceptive outcome measures will be assessed 3 times, and motor outcome measures 4 times, on this day (Fig. 1).

Outcome Measure 1: Proprioception. This will be quantified from a psychometric function, based on a sequence of trials in which the participant estimates their hand position. From the psychometric function we will extract proprioceptive bias (50% point) and sensitivity (distance between 25% and 75% points on the function).

Outcome Measure 2: Motor skill. This will be quantified from the speed-accuracy function, based on the person's in-track accuracy when tracing the maze at three different speeds. Shifts in the speed accuracy function (better accuracy at any of the movement speeds) indicates motor skill learning.

**Fig. 1.** Session design of the main (experimental) session, which takes place on a single day. Proprioception and motor skill will be assessed at multiple time points.

## 4.0 Eligibility Criteria

### 4.1 Inclusion Criteria

- Between the ages of 18-45 years old. Aging has been shown to affect the morphology of sensory and motor nerves, conduction velocities of nerves, and number of motor neurons in the spinal cord; to avoid these confounding factors we will only examine younger-to middle-aged adults.
- Right-handed. There are differences in cortical function and corticospinal projections such that testing the right arm of a right-handed individual is not necessarily equivalent to testing the left arm of a left-handed individual. To eliminate this confound, we will only test right-handed individuals.
- Covid has been found to have neurological effects in some people, but mostly the effects on sensorimotor control and neurophysiology are unknown. We will only include individuals who report being free of Covid symptoms in week preceding testing.

[figure not shown]
### 4.2 Exclusion Criteria

- Any past or present history of neurological disorders, heart or respiratory disease, hypertension, brain injury, spinal cord surgery, or metal implants in the head.
- Orthopedic or pain conditions.
- Pregnant or think they might be pregnant.
- Lack of normal vision or corrected-to-normal vision with contacts or glasses.
- Subjects will also be excluded if they currently suffer from frequent severe headaches, glaucoma, heart or respiratory disease, hypertension, psychiatric conditions, or learning or attention conditions.
- They will also be excluded for current or past: visual, hearing, or balance impairments; stroke, seizure/epilepsy (including family history), or severe head trauma; fainting; or diabetes.
- Subjects will be excluded for metal implants in the head other than titanium; cochlear implants; implanted neurostimulator; cardiac pacemaker; intracardiac lines; or a medication infusion device.
- Because TMS does not penetrate deeply into the head, we cannot test subjects whose hair does not permit contact between the TMS coil and the scalp. We will therefore exclude subjects with dreadlocks, weaves, or hair extensions.
- To protect the data from extraneous peripheral influences, we will also exclude subjects who have had serious injury to the bones, joints, or muscles of either hand or arm, and have not fully recovered. For the purpose of this study, "fully recovered" means they no longer notice any pain, weakness, or loss of sensation in the injured area, and have no mobility limitations.
- Taking medications or drugs that are known to affect cortical excitability and possibly seizure risk in an rTMS study. These medications/drugs are (Rossi et al., 2009): imipramine, amitriptyline, doxepine, nortriptyline, maprotiline, chlorpromazine, clozapine, foscarnet, ganciclovir, ritonavir, amphetamines, cocaine, (MDMA, ecstasy), phencyclidine (PCP, angel's dust), ketamine, gamma-hydroxybutyrate (GHB), theophylline, mianserin, fluoxetine, fluvoxamine, paroxetine, sertraline, citalopram, reboxetine, venlafaxine, duloxetine, bupropion, mirtazapine, fluphenazine, pimozide, haloperidol, olanzapine, quetiapine, aripiprazole, ziprasidone, risperidone, chloroquine, mefloquine, imipenem, penicillin, ampicillin, cephalosporins, metronidazole, isoniazid,

levofloxacin, cyclosporin, chlorambucil, vincristine, methotrexate, cytosine arabinoside, BCNU, lithium, anticholinergics, antihistamines, sympathomimetics.

- Claustrophobic, or are unable to remain still for long periods of time; or use an intra-uterine device (IUD) who's MR compatibility has not been established.
- People who have a BMI over 30 will be excluded as it may be uncomfortable or impossible to lay in the MRI scanner.
- Potential subjects will be invited to reschedule if they would otherwise be eligible (according to the initial screening), but the day of testing have drunk more than 3 units of alcohol or taken other recreational drugs in the 24 hour period prior to testing; have had more than 3 cups of coffee in the last hour; are sleep deprived (<4 hours sleep the previous night); or have participated in another brain stimulation experiment the same day.
- In addition, we will invite subjects to reschedule if they have any of the common Covid symptoms within the last week.
- After giving their consent, participants may be excluded during or after the familiarization session if they are unable to perform the reaching task or follow instructions, or if their TMS stimulation parameters cannot be reliably determined by the experimenter, or if TMS is not well tolerated.

## 5.0 Study Design

## 6.0 Enrollment/Randomization

Potential subjects will initiate contact with the research staff in response to the recruitment flyers. The subject will be given information about what the experiment entails and will be asked questions to make sure they meet the inclusion/exclusion criteria. If they are interested in participating and meet the inclusion/exclusion criteria, then they will be scheduled for their first session (familiarization session) which will take place in the Sensorimotor Neurophysiology Laboratory, [name].

At the familiarization session, before any experimental procedures occur, a research team member will explain the procedures in more detail and go through the consent form with the subject. The subject will then have the opportunity to ask any questions and read the informed consent before signing. After the familiarization session, if the subject was not bothered by TMS and wants to continue, random group assignment will occur, following a block randomization table. There will be 3 groups that differ in cTBS intervention and amount of motor skill practice. Subjects will have a 67% chance of receiving cTBS, and a 33% chance of receiving sham cTBS (details below).

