## 7.0 Study Procedures

All procedures are conducted for research purposes only. The study will be comprised of a familiarization session, an anatomical MRI brain scan session (except for those assigned to a sham group) and one experimental session. Subjects will be offered the option to combine their familiarization session and MRI scan or MRI scan and experimental session in the same day for a total of 2 lab visits or on separate days for a total of 3 lab visits. (Table 1). All study procedures will take place in the Sensorimotor Neurophysiology Lab, SPH 079 and the MRI scan will take place in the Imaging Research Facility in the Psychology building.

**Table 1.** Study structure. TMS = transcranial magnetic stimulation, cTBS = continuous theta burst stimulation, MRI = Magnetic Resonance Imaging. TMS is applied over motor cortex. cTBS is applied over DLPFC or SMG.

Session	Procedures	Proceed to next session if...
Familiarization	TMS, motor skill task, proprioception assessment	Subject comfortable with TMS, can follow task instructions, and wants to continue
MRI anatomical scan	Anatomical scan of the brain – dependent on group assignment	Subject wants to continue
Main Session	TMS, cTBS, proprioception and motor skill assessments, motor skill practice.	End of experiment

The familiarization session involves transcranial magnetic stimulation (TMS) over the motor cortex, a motor skill task that involves a series of tracing movements with the right arm, and a position sense task that involves a series of judgements about the location of their right-hand position. First, subjects will fill out a TMS screening form. Upon confirming eligibility, subjects will sit in a comfortable chair while a non-invasive brain stimulation device (the TMS coil) is held over their head. We will deliver brief magnetic stimuli over the motor cortex that evoke a small twitch in their hand muscles. Subjects will wear a pair of goggles that enable accurate positioning of the TMS coil relative to the

head (Brainsight Neuronavigation system) and have stick-on sensors on their hand to measure their muscle activity upon stimulation. This will take approximately 20 minutes.

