For the motor skill task and the position sense task, they will sit in a comfortable chair and view the task display in a mirror while grasping a robotic manipulandum handle (BKIN) in their right hand (Fig. 2). During the motor skill task, they will guide a cursor representing hand position through the displayed maze. The hand feedback will be given using a visual cursor (10 mm diameter white circle). This design is similar to Mirdamadi and [name] (2020) with six straight line segments connected in abrupt corners (Fig. 2, left). Subjects will move the cursor into a red square at the start of the trial. The square will turn green after 1s, and the maze track will appear with another green square at the end of it. The participants will be instructed to reach the second target at the end of the track by moving the white cursor within the track as accurately as possible. The trial ends when the cursor enters the second target at the end of the maze. Feedback will be given about their movement time (too fast, too slow, good speed) and accuracy with points. The desired speed range will change during the speed-accuracy tradeoff assessment. The maze will be performed over three movement times (MT) ranges to assess the speed-accuracy tradeoff in three blocks of trials (MT 1: 600 – 850 ms; MT 2: 850 – 1100 ms; MT 3: 1100 – 1400 ms). 10 trials will be performed in each MT range and the block order will be randomized. The maze tracing will be standardized meaning the same maze will be used for all the trials between subjects.

During the position sense task, the participant's hand will be passively moved by the robotic manipulandum to two different positions. Participants will be asked to report whether the second position is closer to their body than the first position. An adaptive staircase algorithm is used to determine the test positions with a 0.5 cm step size. There will be 82 trials in total each time and the test will be standardized across participants.

The motor skill and position sense assessments will take approximately 30 minutes. If subjects are comfortable with all procedures and can follow task instructions, they will be assigned to a group. This group assignment will decide whether they need an anatomical brain scan.

[figure not shown]

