Figure 2. Setup for behavioral procedures. Participant holds handle of robotic manipulandum with right hand and makes arm movements to targets presented in visual display (motor skill task) or judges where handle is moved in relation to a target (position sense task).

primary motor cortex with TMS (Caulfield et al., 2022; Nieminen et al., 2022). The main session includes all the same elements as the familiarization session (TMS, proprioceptive assessment, motor skill task), plus cTBS. After the first motor skill assessment and proprioception assessment (Fig. 1), we will deliver single pulses of magnetic stimuli over the motor cortex and determine the resting motor threshold (RMT) as the lowest TMS intensity that elicits a muscle twitch of at least 50 microvolts at least 10 times out of 20 (Rossini et al., 2015). We will then deliver cTBS in the standard pattern (600 pulses over 40 seconds, at an intensity of 70% of RMT). For non-sham groups the coil will be positioned over DLPFC or SMG, as determined by the Brainsight neuronavigation system. For sham groups, the coil will be tilted 90 degrees so the magnetic field is not directed into the head; they hear the clicking noises but no current is induced in the brain (Rossi et al., 2009). Then, subjects will perform second pair of assessment tasks. This will be followed by practice of the maze tracing task for about 20 minutes, with a motor skill assessment partway through. Practice of the maze task will occur at a single MT range (MT 2). The session will conclude with the third pair of assessment tasks.

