## 8.0 Study Calendar

	Familiarization Session	MRI session if needed	Main Session
	First visit	Second visit	Second or third visit
STUDY PROCEDURES			
In person screen, Consent and Handedness questionnaire	X		
TMS tolerance check	X		
Practice Behavioral tasks	X		
Random group assignment	X		
In person Screening		X	X
cTBS			X
Position sense assessment task			X
Motor skill assessment task			X

	Familiarization Session	MRI session if needed	Main Session
	First visit	Second visit	Second or third visit
Motor skill practice			X

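### The stimulation site is drawn after familiarization but not used until coil placement, so exclusions and losses in between are post-randomisation events in the DLPFC-versus-SMG comparison

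*Combined protocol and SAP*

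**What the plan says.** Section 6.0 states that, once the participant has tolerated TMS at familiarization and wishes to go on, "random group assignment will occur, following a block randomization table". The Section 8.0 calendar agrees: the row "Random group assignment" is marked only under the first visit.

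Section 7.0 gives the one early use of the assignment: "This group assignment will decide whether they need an anatomical brain scan". Beyond familiarization the study comprises "an anatomical MRI brain scan session (except for those assigned to a sham group) and one experimental session", so both active groups are scanned and sham is not.

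For the main session Section 7.0 says: "After the first motor skill assessment and proprioception assessment (Fig. 1), we will deliver single pulses of magnetic stimuli over the motor cortex". This gives the resting motor threshold (RMT), and cTBS follows at 70% of RMT. The note to Table 1 separates the two kinds of stimulation: "TMS is applied over motor cortex. cTBS is applied over DLPFC or SMG".

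Participants can still leave after the draw. Section 4.2 allows exclusion during or after familiarization, among other reasons "if their TMS stimulation parameters cannot be reliably determined by the experimenter". Section 11.0 adds withdrawal for not managing the task instructions, exclusion when TMS measurements fail, and rescheduling. Table 1 makes progress beyond the MRI depend on the participant's wish.

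**The concern.** An allocation is best opened as late as the procedures allow, because whatever happens between the draw and the intervention happens to people who already belong to an arm. Here the draw fixes more than is needed at the time. Scan or no scan must be known early; DLPFC or SMG need not be.

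Section 2.0 names the difference between the DLPFC and SMG groups as part of what the study is to establish, alongside their differences from sham. If someone assigned to one site is excluded because TMS parameters could not be settled, is rescheduled, or drops out after the scan, that event belongs to one arm of this comparison. Staff who knew the site could, without intending it, exercise discretion differently. No analysis can fully repair selective loss of this kind. The available text also does not say how participants lost after assignment are analysed.

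**Working it through.** **The plan's own figure.** The timing point has no figure in the documents. The nearest is the sample size in Section 12.0: f = 0.14, alpha 0.05, power 0.8, 24 per group. The correlation between timepoints is not given; 0.5 is assumed. For a repeated-measures group-by-time interaction under sphericity, with k groups, m timepoints, total N and correlation rho:

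- lambda = f² × N × m / (1 − rho), df1 = (k − 1)(m − 1), df2 = (N − k)(m − 1).
- Six cells (3 stimulation types × 2 durations), m = 3, N = 6 × 24 = 144: lambda = 0.0196 × 144 × 3 / 0.5 = 16.93; df 10 and 276; power 0.804. The smallest n reaching 0.8 is 24, so the figure reproduces on this reading.
- Three groups (N = 72), rho 0.5: power 0.616 with m = 3 and 0.691 with m = 4. The stated power then needs a correlation of roughly 0.60 (m = 4, power 0.802) to 0.65 (m = 3, power 0.791).
- Six cells with only the three-way interaction degrees of freedom (df1 = 2 × 1 × 2 = 4), m = 3, rho 0.5: power 0.923.

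The documents do not show which reading was used. Moving the site draw changes none of these figures.

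**Order of steps, and whether each needs the site.**

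| Step | Source | DLPFC versus SMG needed? |
|---|---|---|
| Familiarization, task and TMS checks | 6.0, 7.0 | No |
| Full group draw | 6.0, 7.0, 8.0 | Only scan or no scan is used |
| MRI (both active groups) | 7.0 | No: same anatomical scan |
| Repeat screening | 8.0 | No |
| Baseline motor and proprioception pair | 7.0 | No: same tasks |
| RMT over motor cortex | 7.0 | No: same target and rule |
| Coil placement for cTBS | 7.0 | Yes: first use |

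Neuronavigation targets must be marked beforehand, but both can be marked for every active participant.

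**Size of the exposed interval (illustration).** No loss rate is stated; 5-10% between draw and cTBS is assumed.

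- Per group of 24: 24 × 0.05 = 1.2; 24 × 0.10 = 2.4.
- If 24 is the size of each of six cells, each site has 2 × 24 = 48: 48 × 0.05 = 2.4; 48 × 0.10 = 4.8.
- Power on the six-cell reading: 24 × 0.95 = 22.8, rounded to 23 per cell, gives 0.783; 24 × 0.90 = 21.6, rounded to 22 per cell, gives 0.759, against 0.804 with no loss.

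The fall in power comes from the loss itself, not from the timing of the draw. Timing decides whether the loss can differ by site. With a late draw, no loss before cTBS can, because no site has been assigned.

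**The case against.** The case for leaving the plan as it is has real substance.

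- **Early assignment has a reason.** The group decides who is scanned. Drawing only after TMS has been tolerated and the tasks managed already puts much attrition before randomisation. MRI-related exclusions (claustrophobia, BMI, IUD) are general criteria asked about before the first visit, so later screening is a repeat check. This stands, but it justifies an early scan decision, not an early site decision.
- **Staff knowledge is not documented.** A reader might infer that the operator knows the site throughout baseline and RMT, or can foresee the next allocation from the block table. The documents do not say who holds the table, who sees the group or what the block size is. Section 5.0 shows no text, and the part of Section 7.0 leading into the main session begins mid-sentence, so concealment, or an earlier use of the site, may be described in text not available here. Neither inference can be stated as fact.
- **Baseline and intensity are weak routes.** A reader might infer that knowing the site would distort the baseline or the cTBS intensity. Position sense is tested by passive robot movement with an adaptive staircase and 82 trials, the maze is the same for everyone, and RMT has a set rule (50 microvolts in 10 of 20). For scale, a reading 1-2 points of stimulator output off at an assumed RMT of 50 would move intensity by 1/50 = 2% to 2/50 = 4%. Such error can occur whether or not the arm is known, and nothing shows it would differ between sites.
- **Losses may be balanced.** Both active groups go through identical steps before cTBS, so loss should be much alike unless someone acts on the site. That is fair, and it is why this is a risk and not a demonstrated bias.
- **Protection is partial.** Section 2.0 relies heavily on comparison with sham, and whether a scan is booked still separates active from sham. Post-cTBS assessments also follow coil placement. Both limits stand.

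**Conclusion.** The point holds as a modest, avoidable weakness. The full group is drawn after familiarization although only the scan decision is needed then; in the available text the site has no use until coil placement. Exclusions, rescheduling and withdrawals in between are post-randomisation events for DLPFC versus SMG, and nothing available keeps the site from staff during that time. Discretionary exclusion and loss are the main route; baseline and RMT are minor.

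Its size cannot be fixed from the documents. The 1.2 to 2.4 per 24 rests on an assumed 5-10% loss and counts exposed participants; it does not measure bias. A reader might infer that a late draw would secure the whole trial. It would not: losses after the scan decision remain post-randomisation losses against sham. The conclusion assumes that no missing text gives the site an earlier use or already conceals it. If staff are in fact kept unaware, one sentence saying so would settle most of it.

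**What to change.** Amend Section 6.0 and the calendar so that assignment has two steps.

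1. **After familiarization, once the eligibility decision is recorded:** draw only scan versus no scan, 2:1, from a list hidden from whoever runs familiarization.
2. **In the main session, once the baseline pair and RMT are recorded:** open a concealed draw, sealed or electronic, of DLPFC versus SMG, 1:1 among scanned participants. Mark both targets in the neuronavigation file beforehand.
3. **Practice duration:** Section 6.0 describes 3 groups differing in cTBS and amount of practice, while Section 12.0 crosses three stimulation types with two durations. Reconcile these first, then state at which step duration is assigned and balance the site draw within it.

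Split the calendar row to show both steps. The cost is a second draw and one extra target marked per active participant, plus the wording change; no added scans, staff or participants. The change does not protect active-versus-sham comparisons and does not blind the operator once the coil is placed.
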